## ABBREVIATIONS AND LIST OF DEFINITIONS OF TERMS

Abbreviation	Term/Definition
Akt	A growth factor pathway component (serine-threonine kinase)
Alk Phos	Alkaline phosphatase
ALT	Alanine aminotransferase
ANC	Absolute neutrophil count
AST	Aspartate aminotransferase
ASCO/CAP	American Society of Clinical Oncology/College of American Pathologists
CBC	Complete blood count
CCCA	Complete cell cycle arrest (Ki67≤ 2.7%)
CDK	Cyclin-dependent kinase
DL	Dose level
DLT	Dose-limiting toxicity
DNA	Deoxyribonucleic acid
ECOG	Eastern Cooperative Oncology Group
ER	Estrogen receptor
ESR1	Estrogen receptor-alpha gene
FDA	Food and Drug Administration (United States)
FSH	Follicle stimulating hormone
HCQ	Hydroxychloroquine
HER2	Human epithelial receptor-2 (HER2/neu)
JAK/STAT	Janus kinase/signal transducers and activators of transcription
Ki67	Kiel antigen, a cellular marker for proliferation
L	Letrozole
LH	Luteinizing hormonal
MBC	Metastatic breast cancer
MCF7	A hormone receptor-positive breast cancer cell line
mg	Milligrams
mTOR	Mammalian target of rapamycin
P	Palbociclib
p.o.	By mouth
PR	Progesterone receptor
PI3K	Phosphoinositide 3-kinase
PIK3CA	Phosphatidylinositol-4,5-Bisphosphate 3-Kinase Catalytic Subunit Alpha
Rb	Retinoblastoma protein
RNA	Ribonucleic acid
RP2D	Recommended phase II dose
SEER	Survey End Epidemiology Results
SMC	Safety and Monitoring Committee
T. Bili	Total bilirubin
ULN	Upper limits of normal (Institutional)
U/S	Ultrasound

## 1.0 Introduction

### 1.1 Background

#### 1.1.1 Hormone receptor-positive breast cancer

Breast cancer is the most common female cancer in the United States. It is estimated that 252,710 American women will be diagnosed with breast cancer and 40,610 will die from the disease in 2017. A major cause of death in these patients is disease progression and incurable metastasis. The SEER database estimates that ~40,000 breast cancer patients a year either present at diagnosis (n=13,900) with metastatic disease or exhibit progression with metastatic disease, sometimes many years after completing therapy for early stage disease (n=36,000). Of these, an estimated 30,000 have estrogen receptor (ER)-positive breast cancers. Hence, patients with ER+ metastatic breast cancer (MBC) represent a majority of breast cancer who die of their disease, the vast majority due to metastatic progression.

#### 1.1.2 Therapies for hormone receptor-positive breast cancer

In early stage estrogen receptor-positive (ER+) breast cancer, the use of adjuvant endocrine therapy (tamoxifen or aromatase inhibitors) lowers the relative risk of recurrence at 10 years by 45 to 50% and that of mortality by breast cancer death by 30%. In the metastatic setting endocrine therapy can induce responses and delay progression of disease. However, in the metastatic setting, it has been difficult to demonstrate a survival benefit of endocrine therapy. Few modern-day trials have compared endocrine therapy to no endocrine therapy in the absence of chemotherapy since treatment induces clear palliation. More recent trials comparing single-agent to combination endocrine therapy agents (e.g. aromatase inhibitors plus the ER down regulator fulvestrant) have yielded mixed results. In the last few years, the addition of biological therapies that were designed to address mechanisms of resistance or with demonstration of preclinical synergy have shown improvements in disease-free survival when added to endocrine therapy, but no impact on overall survival - although these trials were not designed with the statistical power to survival differences, with disease-free survival designated as the primary endpoint. The addition of the mTOR inhibitor everolimus doubled median disease-free survival from 4.1 to 10.6 months when added to the aromatase inhibitor exemestane as second-line therapy and was approved by the FDA with final survival analysis showing no significant difference in that outcome (median survival of 31.0 vs. 26.6 months). Other biological agents such as PI3 kinase inhibitors, histone deacetylase inhibitors and cyclin-dependent kinase CDK) inhibitors are being actively tested in first, second and later lines of therapy - so far CDK 4/6 inhibitor palbociclib has been approved by the FDA as outlined in the next section.

In summary, this is a novel investigator initiated study funded by CPRIT grant which aims to evaluate the safety and tolerability (phase I) of adding HCQ to continuous low dose palbociclib and letrozole in metastatic HR+, HER2- breast cancer and thereafter determine whether the inhibition of autophagy with HCQ can decrease proliferation index in a window study (Phase II) in postmenopausal women with stage I-III HR+/HER2- breast cancer. The scientific rationale is based on preclinical work that has been done by the trial investigators and published as is well described in the protocol. Further the trial has been vetted through our departmental HR positive working group as well our department's protocol review process. A multidisciplinary team of collaborators are involved and it is well funded. Finally, we have had success with accrual demonstrated to other window trials, with several such studies ongoing without any concerns of low accrual. As noted in the trial prioritization, this is #3 of 5 trials in the HR+, HER2- patient population but the other ongoing or planned trials are expected to have little if any overlap with the activation of protocol 2017-0071.

### 1.1.3 Palbociclib and use in breast cancer

Palbociclib is a potent and specific cyclin-dependent kinase 4/6 (CDK4/6) inhibitor and anti-proliferative agent that induces G1 arrest and prevents breast cancer cell growth, most notably in ER+ cell lines and other preclinical models, which led to the clinical development of this class of inhibitors in hormone receptor-positive breast cancer. Palbociclib was approved by the FDA in February, 2015 based on improved time to disease progression in the first and second-line settings for ER+/HER2-negative metastatic breast cancer (MBC). In the pivotal first-line Phase III trial, progression-free survival (primary endpoint) was improved from 14.5 to 24.8 months with the addition of palbociclib to the standard first-line aromatase inhibitor letrozole. In the second-line setting, the addition of palbociclib to the standard second-line estrogen downregulate fulvestrant in a Phase III trial also demonstrated a significant improvement in time to progression from 3.8 to 9.2 months.

[figure not shown]
However in the first line setting, 66% of patients on the palbociclib experienced grade 3 and 4 neutropenia, and adverse events necessitate a palbociclib dose reduction in 36% and discontinuation in 7.4% of patients. Additionally, palbociclib must be dosed with a 7-day break, which was shown to be associated with a proliferative burst in a separate neoadjuvant serial biopsy study. Also, a precise biological mechanism of palbociclib's action is still unknown and there are no known independent biomarkers to predict response and/or resistance to palbociclib – many patients do not respond to therapy, and most importantly, virtually all eventually develop resistance. Biomarkers that may influence response to endocrine therapy and CDK inhibitors including estrogen receptor-alpha (*ESR1*) and *PIK3CA* mutations, loss of the retinoblastoma protein function, proliferative antigen Ki67 expression, *cyclin D1* gene amplification or loss of the cyclin-dependent kinase inhibitor p16 have not shown to be related to palbociclib-associated response or time to progression. Importantly, no survival benefit yet observed in either of the larger randomized trials or smaller Phase II trial, although these trials were not powered for survival differences and diversity of therapies that patients may receive in their subsequent management may cloud future survival update analyses.

## 1.2 Mechanisms of Resistance to Endocrine Therapy and Rationale for the use of Autophagy inhibition with Hydroxychloroquine

While specific mechanisms of resistance to palbociclib have not been well characterized, there are several mechanisms of resistance to conventional endocrine therapies such as tamoxifen and aromatase inhibitors, which include activation of receptor tyrosine kinase signaling pathways (notably the PI3K/Akt/mTOR pathway), activation mutations in *ESR1* and other more general alterations such as epigenetic regulation of gene expression other intersecting pathways like NFKB and JAK/STAT. As described earlier, mTOR and CDK4/6 inhibition with everolimus and palbociclib are now approved as biological agents in combination with endocrine therapy, while strategies using inhibitors of PI3K, Akt, histone deacetylase are undergoing testing, none so far has been able to induce durable enough responses to affect survival, and clinical resistance still emerges with all available therapies.

Our laboratory research group, led by [name], Professor of Experimental Radiation Oncology at MD Anderson, has an extensive investigational track record in area the cell cycle pathways in breast cancer. We have shown that at low concentrations of the palbociclib, ER+ breast cancer cells arrest in the G1 phase of the cell cycle, but this arrest is reversible due to the activation of autophagy. However, at high concentrations of palbociclib, the cells are arrested irreversibly in G1, do not undergo autophagy and instead undergo senescence. The low concentration of palbociclib are on-target and are specific for inhibition of CDK4 and CDK6, as shown with siRNA assays where CDK4 and CDK6 where knocked down. The high concentrations of palbociclib, induce senescence, but these are off target effects of the drug. We also demonstrated that if we combine palbociclib with an autophagy inhibitor such as hydroxychloroquine (HCQ), we can achieve senescence at a much lower (i.e. on- target) and continuous dosing of palbociclib, in both *in vitro* and *in vivo* models. Moreover, concomitant treatment with HCQ and palbociclib can mediate a synergistic response in ER+ xenograft (MCF7) mouse tumor volume and weight compared to palbociclib alone. More strikingly, the tumor volumes with combination treatment did not increase even after the treatment was stopped, while the tumor volumes with either palbociclib or HCQ alone continuously increased during both the treatment and recovery phases of the experiment. Combination treatment showed the desired and expected impairment in autophagic flux. Decrease in Rb phosphorylation, a direct readout of CDK 4/6 inhibition, was more pronounced with the addition of HCQ. These results suggest that autophagy inhibition significantly improves the efficacy of low dose (on target) palbociclib *in vivo* and facilitates the induction of an irreversible tumor growth inhibition. We propose that palbociclib activates the autophagy pathway to protect ER+ breast cancer cells from palbociclib-induced senescence and inhibition of autophagy sensitizes cells to lower doses of palbociclib *in vitro* and *in vivo* (Figure 1).

**Figure 1: Model for Hydroxychloroquine to Inhibit Autophagy and Potentiate Palbociclib**

demonstrate enhanced anti-proliferative effect. An anti-proliferative effect of endocrine therapy using quantification of the proliferative Ki67 antigen has been validated as a long-term predictor of outcome. HCQ is a commonly used and generally safe drug used to treat malaria and as a remittive agent for various autoimmune diseases (see more expanded description in Section 6.2). This trial will therefore provide evidence of a promising therapeutic effect with lower dose palbociclib plus letrozole for a greater therapeutic effect with less side effects. This is needed before proceeding with a more definitive trial that could be potentially practice-changing.

### 1.3 Rationale for the Use of Pre-operative (Neoadjuvant) or “Window” Endocrine Therapy

We have chosen to perform this trial using the combination of letrozole, palbociclib and HCQ in the pre-operative (neoadjuvant) “window” setting after careful deliberation internally and advice

from both internal and external advisory board members during the process of a grant proposal submission that led to the successful funding of both the laboratory and clinical trial aims of this project. However, the initial lead-in Phase I safety trial that includes HCQ dose escalation with the study regimen of continuous low dose palbociclib and letrozole and the determination of the recommended Phase 2 dose (RP2D) for HCQ will be conducted in patients with advanced metastatic breast cancer, followed by activation of the neoadjuvant/window trial.

The following rationale support this approach:

- Palbociclib is already FDA-approved for metastatic breast cancer with an excellent safety record. It is currently in several clinical trials in both the neoadjuvant and adjuvant settings.
- Treatment will include letrozole, a standard endocrine therapy as is used clinically for early stage breast cancer.
- HCQ is an approved drug commonly used for malaria and autoimmune disease and particularly safe when used at the doses and timeframes proposed (see more expanded description in Section 6.2).
- This model allows for safe biopsies as needed for the correlative tissue aims and eliminates artifact and variability due to prior therapies as all patients will be previously untreated.
- The design gives patients and their physicians the option of a brief “window” trial with 4 weeks on study drug (2 weeks on low dose palbociclib plus letrozole, then 2 weeks with the addition of HCQ) then to proceed with surgery or a research biopsy if additional standard of care neoadjuvant therapy is indicated, and then followed by standard of care.
- The very first exposure to the combination will be performed in a cohort of patients with advanced breast cancer using a standard “3+3” Phase I HCQ dose escalation scheme in combination with the study regimen of low dose continuous palbociclib with letrozole. Once safety is established at the specific HCQ dose level, the corresponding arm of the Phase II neoadjuvant/window trial will be activated. This approach will maximize safety by only moving to early stage curable population once safety of the study regimen is established in the advanced setting.

There is ample clinical experience and clinical trial to support the use of neoadjuvant endocrine therapy as method to downstage tumors and allow more patients to undergo breast-conserving surgery. Additionally, the neoadjuvant model is a well-established research tool to assess newer drugs when added to endocrine therapy to evaluate both clinical as well as biomarker based-responses. For hormone receptor-positive and HER2-negative breast cancer, the use of change in the proliferative antigen Ki67 pre to post treatment has been extensively validated as index that correlates with the likelihood of achieving a complete pathological response and with longer term outcomes specifically in trials. The key metrics using this model are obtained after 4 weeks of low dose Palbociclib and HCQ (safety) in the Phase I portion and after 2 weeks of low dose palbociclib and then 2 additional weeks with the addition of HCQ (efficacy) in the Phase II portion (see Sections 2.0 and 3.1).

Therefore, patients can come off study after 4 weeks and proceed with standard therapy (“window” approach), which would include standard neoadjuvant endocrine therapy (typically aromatase inhibitor), neoadjuvant chemotherapy if the patient is known to have the stage, grade and other indices that warrant chemotherapy. Alternatively, they can proceed with definitive breast/axillary node surgery. In addition, if the biopsy after both 2 and 4 weeks show suppression of proliferative index that is used as the main endpoint of the study (see Section 2.2.1), patient can stay on therapy for the typical full neoadjuvant endocrine therapy course which is typically 16-24 weeks.

These pragmatic alternatives will maximize accrual and allow patients and their physicians to opt for the best path that matches the patient's clinical situation.

#### **1.4 Risk/Benefit Assessment**

Patients on this study will be receiving standard of care therapy (endocrine therapy with letrozole) and palbociclib, an FDA-approved and relatively non-toxic therapy that doubles time to progression in the metastatic setting, but not approved in the adjuvant or neoadjuvant setting (see additional description of palbociclib in Section 6.1). HCQ is an approved drug used for malaria and autoimmune disorders that also had a very good safety profile (see additional description of HCQ in Section 6.2). One concern of retinal toxicity that is typically seen only after prolonged exposure, will be mitigated by baseline ophthalmological exam covered by the study funding, and exclusion of those who are felt to be at risk for retinal toxicity as established by the American Academy of Ophthalmology to exclude preexisting maculopathy. In order to exclude unexpected toxicities of the proposed combination in patients with early stage breast cancer who may have a reasonably good prognosis and chance of cure, a run-in Phase I safety study will be conducted in patients with metastatic breast cancer who are also candidates for standard palbociclib and letrozole therapy. The experimental regimen proposed for the window/neoadjuvant protocol, low dose continuous palbociclib and standard dose letrozole will be used, in combination with increasing doses of HCQ.

The benefits of participation of this trial cannot be fully ascertained, but the addition of palbociclib has been shown to achieve a high rate of complete cell cycle arrest, a surrogate biomarker of long-term benefit. While short term exposure (4 weeks) may not affect outcome, patients who stay on study for a total of 16-24 weeks prior to surgery may have a greater degree of down staging and more conservative surgery (e.g. breast conservation, sentinel node biopsy as opposed to axillary dissection).

## **2.0 STUDY AIMS AND OBJECTIVES**

The overall study aim is to determine whether autophagy inhibition with HCQ can significantly decrease proliferation index, a validated surrogate of long term outcome, when added to a continuous low dose palbociclib and letrozole.

### **2.1 Phase I Safety Component (metastatic disease) Objectives and Endpoints**

2.1.1 The primary objective of the Phase I portion in the metastatic setting is to determine the safety of adding HCQ to continuous low dose palbociclib and letrozole and to determine the recommended phase II dose for HCQ for the subsequent Phase II study.

Primary endpoint is safety, to be assessed continuously using CTCAE V4.03, with physical examination and laboratory assessments as indicated on the study schedule. Dose-limiting toxicities as defined in Section 3.3.

2.1.2 The secondary objective is to determine the response rate and clinical benefit rate at 8 weeks of the assigned HCQ dose plus continuous low dose palbociclib and letrozole.

## 2.2 Phase II Window/Neo-adjuvant Component Objectives and Endpoints

### 2.2.1 Phase II - Part 1 Primary Objectives and Endpoints

To determine the dose responsiveness of 2 dose levels (400 mg and RP2D) of hydroxychloroquine added to low dose palbociclib and letrozole on pre and post HCQ breast tumor proliferation index (Ki67), autophagy, senescence and cell cycle control.

### 2.2.2 Phase II - Part 1 Secondary and Additional Objective and Endpoints

Determine longer term clinical tumor responsiveness (tumor volume) and tumor biomarker indices (for patients who have extended pre-operative therapy, maximum 24 weeks).

Perform exploratory studies on blood-based tumor protein, DNA and RNA biomarkers with a focus on pathways of cell proliferation, autophagy, senescence and cell cycle control.

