### 2.2.4 Phase II Part 2 Secondary Objectives and Endpoints

- To determine the impact of adding hydroxychloroquine to low dose palbociclib and letrozole on breast tumor indices of proliferation, autophagy, senescence, cell cycle control and other intersecting pathways.
- Determine longer term clinical tumor responsiveness and tumor biomarkers indices (for patients who have extended pre-operative therapy, maximum 24 weeks).
- To determine the dose responsiveness of HCQ (400 mg vs. RP2D) on the primary (proportion with CCCA) and secondary clinical/biological endpoints
- To perform exploratory studies on blood-based tumor protein, DNA and RNA biomarkers.
- Obtain additional safety information for the combination of low dose palbociclib, letrozole and hydroxychloroquine.

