### 5.2 Schedule of Assessments

Table 1 – Study Procedures and Assessments Phase I

	Baseline	C1 W1	C1 W2	C1 W3	C1 W4	C2 W5	C2 W6	C2 W7	C2 W8	C3 W1	C4+ W1	Off Study
Day		D1	D8	D15	D22	D1	D8	D15	D22	D1	D1	
Scheduling timeframe	-14d	+/- 2	+/- 2	+/- 2	+/- 2	+/- 2	+/- 2	+/- 2	+/- 2	+/- 2	+/- 2	Within 30 D
Laboratory	X A	X	X	X	X	X	X	X	X	X	X	X
Adverse event assessment)		X	X	X	X	X	X	X	X	X	X	X
Physical exam/ Weight/Vital signs	X A	X	X	X	X	X	X	X	X	X	X	X
ECOG performance status evaluation	X											
Ophthalmologic Exam	X B											X
Imaging Assessments	X A								X C			
Tumor Biopsy	X C					X C						
Palbociclib		X	X	X	X	X	X	X	X	X	X	
HCQ		X	X	X	X	X	X	X	X	X	X	
Letrozole		X	X	X	X	X	X	X	X	X	X	

Table 2 – Study Procedures and Assessments Phase II

	Baseline	W1	W2	W3	W4	W5	Off Study
Day		D1	D8	D15	D22	D29	
Scheduling Window	-14 D	+/- 2	+/- 2	+/- 2	+/- 2	+/- 2	Within 30 D
Laboratory	X A	X	X	X	X	X	X
Adverse event assessment)		X	X	X	X	X	X
Physical Exam/Weight/Vital Signs	X A	X	X	X	X	X	X
ECOG performance status evaluation	X	X	X	X	X	X	X
Ophthalmologic Exam	X B						X
Breast ultrasound	X A					X	
Research blood	X A			X		X	X
Biopsy (or surgery)	X A			X		X D	
Low dose palbociclib + letrozole		X	X	X	X		
HCQ				X	X		

Abbreviations: W=week (week 1 is the same as day 1 prior to starting palbociclib); HCQ = hydroxychloroquine; D = day; W = week

Laboratory assessments: Baseline, then weekly x 8 for Phase I and x 4 for Phase II, then as indicated until off study labs include CBC/differential, electrolytes, BUN, creatinine, glucose, albumin, AST, ALT, total bilirubin, alkaline phosphatase. Baseline only: PT, PTT, urinalysis with microscopic exam. Baseline urine or serum pregnancy test for both Phase I and II.

Superscripts:

A= Phase I: Laboratory assessment must be done within 14 days of C1 D1. Any imaging assessments already completed during the regular work-up of the patient within 28 days prior to starting study treatment, including before signing the main study ICF can be considered as the baseline images for this study; Phase II: done within 2 weeks prior to starting therapy (low dose palbociclib/letrozole).

B= done within 8 weeks prior to starting study medication

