### 5.2.2 Evaluation During Study Phase II

Patients will be evaluated with an organ-specific review of systems and physical exam at weeks 2, 3, 4, and those who choose and are eligible to go beyond the “window period” (as described in Sections 1.3, 3.2.2 and 5.2-Table 2) and stay on study until definitive surgery at week 16 to 24 will undergo additional evaluation at weeks 6, 8 and every 4 weeks thereafter until the last pre-operative visit between week 16 and 24 at the discretion of the medical and surgical oncologist as shown on Table 2.

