### **5.2.9 Imaging assessments Phase II**

Methods for ultrasound evaluation and volumetric measure of response

Grayscale and power Doppler ultrasound will be performed on the breast and regional nodal basins using a Philips iU22 system or Sonoline Antares systems equipped with a 5- to 13-MHz broadband linear transducer. Ultrasound images of the index tumors and index nodes will be captured in the longitudinal and transverse planes with three dimensions measured. The size of the index tumors and index nodes will be reported in three dimensions to allow for volumetric calculation. The percent change in volume will then be calculated and reported to determine response.

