### **5.3.2 Whole Blood/Plasma Biospecimens**

Blood specimens (Phase II only) will be collected as shown on Table 2 at baseline, days 15 and 29 for patients on the “window” option and for those who stay on study until surgery will be collected on days 43, 57 and every 4 weeks thereafter until surgery. Each blood draw will be to collect three tubes – one for plasma (8 mL CPT top) and the other for serum (6 mL red top) and one for whole blood (6 mL lavender). Blood will be processed immediately following collections – tubes will be gently inverted and kept at room temperature prior to centrifuging, and clotted tube (red top) will have serum aspirated, while the green top tube will have plasma aspirated – both being aliquoted in 0.5 mL cryovials and placed in a -20°C freezer (and stored long term at -80°C). A laboratory protocol contains additional details.

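### Longer-term tumour volume (up to 24 weeks) is a Part 1 secondary endpoint, but Table 2 and Sections 5.2.2 and 5.2.9 set no volumetric ultrasound after day 29

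*Combined protocol and SAP*

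**What the plan says.** - **Part 1 objective, Section 2.2.2.** "Determine longer term clinical tumor responsiveness (tumor volume) and tumor biomarker indices (for patients who have extended pre-operative therapy, maximum 24 weeks").
- **Part 2 objective, Section 2.2.4.** "Determine longer term clinical tumor responsiveness and tumor biomarkers indices (for patients who have extended pre-operative therapy, maximum 24 weeks"). Volume is not named here.
- **Method, Section 5.2.9.** Index tumours and index nodes are measured by ultrasound in three dimensions, and "The percent change in volume will then be calculated and reported to determine response". No time points are given.
- **Schedule, Table 2 in Section 5.2.** The "Breast ultrasound" row is marked at baseline and at W5 (D29). The Off Study cell is blank, and no other column follows W5.
- **Extended visits, Section 5.2.2.** "Patients will be evaluated with an organ-specific review of systems and physical exam at weeks 2, 3, 4". Those who stay on study until later surgery "will undergo additional evaluation at weeks 6, 8 and every 4 weeks thereafter until the last pre-operative visit between week 16 and 24". The section refers to Table 2 and to Section 3.2.2, where Figure 2 stands.
- **Other assessments on the extended course.** Section 5.3.2 sets research blood times: "for those who stay on study until surgery will be collected on days 43, 57 and every 4 weeks thereafter until surgery". Footnote C under the Section 5.2 tables plans a pre-operative biopsy for patients who wait until weeks 20 to 24. Section 5.3.1 has Phase II biopsies done with ultrasound guidance.

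**The concern.** The plan names a quantity, gives a method for measuring it, and then does not say when to measure it at the time that matters. The endpoint concerns patients treated for up to 24 weeks, but the only change in volume that the schedule delivers runs from baseline to day 29. That is a different quantity, because hydroxychloroquine starts at day 15 and the day 29 scan sees two weeks of it.

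Section 1.4 offers greater down-staging after 16 to 24 weeks on study as a possible benefit to patients, and late tumour volume is the measurement that would bear on it. If late scans are left to chance, the patients who have one may differ from those who do not. With 6 patients in Part 1 and 30 in Part 2, and only some of them on extended therapy, a few missing values could decide what is reported.

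**Working it through.** The plan gives no figure to reproduce on this point. The check sets the schedule against the endpoint and then measures the gap.

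**Step 1. Which assessments have a time point after day 29?**

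| Phase II assessment | Time point after D29 for extended patients | Source |
|---|---|---|
| Review visits | Weeks 6 and 8, then every 4 weeks to the last pre-operative visit at weeks 16 to 24 | 5.2.2 |
| Research blood | Days 43 and 57, then every 4 weeks to surgery | 5.3.2 |
| Biopsy | Pre-operative, for those waiting until weeks 20 to 24 | Footnote C, 5.2 |
| Volumetric ultrasound | None stated | Table 2, 5.2.2, 5.2.9 |

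The other extended assessments have times, and ultrasound volume does not. Section 5.2.2 describes the later visits only as additional evaluation, so their content is open. It neither names an ultrasound nor rules one out.

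**Step 2. How long is the gap?** The documents number weeks in two ways.

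- *Table 2 numbering:* week n falls on day 7(n − 1) + 1, so W5 = D29.
  - Week 16: 7 × 15 + 1 = D106; 106 − 29 = 77 days = 11 weeks.
  - Week 24: 7 × 23 + 1 = D162; 162 − 29 = 133 days = 19 weeks.
- *Completed weeks:* week n falls on day 7n + 1. This turns weeks 6 and 8 of Section 5.2.2 into days 43 and 57, the blood days of Section 5.3.2.
  - Week 16: 7 × 16 + 1 = D113; 113 − 29 = 84 days = 12 weeks.
  - Week 24: 7 × 24 + 1 = D169; 169 − 29 = 140 days = 20 weeks.

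Across both conventions, the last scheduled volume precedes late surgery by 11 to 20 weeks. Visit windows of ±2 days do not change this materially.

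**Step 3. How much hydroxychloroquine does the day 29 volume reflect?** Table 2 starts it at D15: 29 − 15 = 14 days.

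**Step 4. Does an ultrasound contact already exist near the endpoint?** Yes, in part. The pre-operative biopsy in footnote C would be done with ultrasound guidance under Section 5.3.1. No three-dimensional measurement is required at it. It is described for weeks 20 to 24, whereas Section 5.2.2 allows surgery from week 16, so 20 − 16 = 4 weeks of the surgical window fall outside its wording.

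**The case against.** The strongest reply is that the schedule may be complete in a place that cannot be read here. The Figure 2 legend defines an abbreviation for ultrasound that it does not otherwise use, so the drawing probably marks ultrasound times. Section 5.2.2 also points to the section that holds it. The missing drawing is a limit of the text available, not a fault in the plan. A reader might infer from Table 2 that no late scan is planned, or that the endpoint cannot be scored in any extended patient. The documents do not support either statement, for this reason and because an ultrasound-guided biopsy is planned at weeks 20 to 24. What remains is that Table 2 and Section 5.2.2 would need to agree with the figure if it does show a scan.

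A second reply concerns scope. Volume is named only for Part 1. Part 2 asks for clinical responsiveness, which the site-focused physical examinations of Section 5.2.6 could inform. It would therefore go too far to say that a named volume endpoint fails in both parts. Even so, Section 5.2.9 offers volume as the Phase II imaging measure of response, so Part 2 benefits from the same clarification.

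A third reply is that the extended group may be empty. Section 5.2.3.2 sends patients after T2 to surgery or to standard of care, whereas Sections 1.3 and 5.2.2 describe staying on study therapy. That conflict is real and must be reconciled. Confirming the extended course would still leave its volume measurement without a date.

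The later-imaging sentence in footnote C does not settle the matter. It speaks of cycles 2 and 3, which are Phase I terms, and Section 5.2.8 repeats the schedule under Phase I.

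**Conclusion.** The concern holds in a limited form. Section 2.2.2 asks for tumour volume on up to 24 weeks of therapy, and Table 2, Section 5.2.2 and Section 5.2.9 set no volumetric ultrasound after day 29. On that schedule the last volume falls 11 to 20 weeks before surgery, depending on how weeks are counted.

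This rests on two conditions: that Figure 2 does not set a later scan, and that some patients do take the extended course. It does not show that late volumes will be absent in every extended patient, only that nothing readable requires them.

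The endpoint is secondary and descriptive, with no hypothesis or sample size attached. The primary cell-cycle-arrest endpoint and its two-stage design are untouched. The point is still worth correcting before enrolment, because a volume not recorded before surgery cannot be recovered.

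**What to change.** Check Figure 2 first, and make Table 2 and Section 5.2.2 agree with whatever it shows. Keep the longer-term objective, since redefining it as change to day 29 would abandon it. Then:

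1. Add a Table 2 footnote and a line in Section 5.2.2. For extended patients, three-dimensional size of the index tumour and index nodes, as in Section 5.2.9, is recorded at the ultrasound-guided pre-operative biopsy already planned in footnote C, or taken from the last pre-operative breast ultrasound if one is done.
2. State that percent change is calculated from baseline.
3. Report change from baseline to day 29 separately, as the short-term measure for all patients who reach T2.
4. Report how many extended patients have a late volume and how many lack one, and limit any long-term claim to those with one.
5. Reconcile weeks 16 to 24 in Section 5.2.2 with weeks 20 to 24 in footnote C, and the extended study therapy of Sections 1.3 and 5.2.2 with the standard of care after T2 in Section 5.2.3.2. Which reading applies is for the sponsor to settle.

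The cost is a few lines of text and three recorded dimensions per lesion at a procedure already planned. The downside is a narrower long-term claim, since patients operated on before week 20 may lack a late volume. The documents do not say whether breast ultrasounds for surgical planning are routine, so the number of late volumes from that source is unknown.
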